Step 1: Identifying relevant records and measures. Relevant state-level TC program records will be identified within the 24 selected states from various sources. First, all state tobacco programs are required by CDC (DP15-1509 funding requirements²) to submit an annual progress report. We will begin by using our consultants and empirical literature to identify relevant state-level programmatic measures documented in these annual progress reports. We have also reviewed the DP15-1509 funding requirements for relevance and have outlined the connection between state reporting requirements and established predictors of sustainability and outcomes in Appendix C. This will increase our likelihood of retrieving all relevant information and provide empirical evidence with which to substantiate the responses in the PSAT and identify and address any potential bias therein. In addition, for those metrics not included in the report, we will review state health agency websites and publically available state-level government documentation. [name] has extensive experience in collecting this type of information and has incorporated similar strategies in three other studies.

Step 2: Data abstraction. TC program records will be reviewed and data will be abstracted by two trained evaluators using standardized methods and data collection tools created by the research team. The development and use of a standardized instrument for the review and abstraction will improve inter-rater reliability and will provide quantitative data for monitoring trends and intervention effects.

Step 3: Establishing reliability and validity. Data collected via record review and abstraction are subject to bias that may result from rater subjectivity.¹⁰⁴ In order to determine the agreement between the two evaluators, a baseline reliability evaluation will be conducted early in the process to calculate inter-rater reliability. In order to determine validity of self-reported data from the PSAT, agreement between self-reported and record-based information will be assessed. Both inter-rater reliability and validity of self-reported data will be checked at baseline and two other time points.

Key Informant Interview and Survey

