In order to collect additional organizational metrics, a key informant interview and survey will be conducted with state program managers. These will be performed for all 24 states at three time points- baseline and in June during years 2 and 3. This will help in evaluating the impact of the training intervention on the capacity for sustainability and institutionalization of the TC program within the organization.

Step 1: Identifying relevant measures. Relevant state-level sustainability metrics will be identified within the 24 selected states from various sources, including CDC Best Practices, ALA State of Tobacco Control, empirical literature, and consultation of our advisory group.

Step 2: Key Informant Interview and Survey. TC program managers will be contacted to complete a phone interview and survey. The interview and survey will only collect organizational metrics not collected in reporting records, and no personal information will be collected. We will record phone interviews to ensure comprehensive analysis by trained abstracters. Prior to the interview, program managers will be provided a copy of the questions to be asked from a standard script created by the research team. Each question is formatted in multiple choice, e.g., “How long has the program been in existence?” [1: Less than 1 year; 2: 1-3 years; 3: 3-5 years; 4: 5-10 years; 5: 10 or more years; 6: Don’t know]. Using this method, program managers will provide unambiguous answers to data points not collected by record abstraction.

Step 3: Establishing reliability and validity. Data collected via interview/survey and abstraction are subject to bias that may result from rater subjectivity.¹⁰⁴ In order to determine the agreement between the two evaluators, a baseline reliability evaluation will be conducted early in the process to calculate inter-rater reliability. In order to determine validity of self-reported data from the PSAT, agreement between self-reported, record-based information, and interview/survey information will be assessed. Both inter-rater reliability and validity of self-reported data will be checked at baseline and two other time points.

Phase 3 (Aim 3):

C.7. (Aim 3): Actively disseminate The Program Sustainability Action Planning Model and Training Curriculum materials and study results to support future adoption.

[figure not shown]
No treatment with intervention or comparison groups will take place during this phase.

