Data abstraction. State level TC program records will be reviewed and data will be abstracted by two trained evaluators using standardized methods and data collection tools created by the research team. Examples of variables of interest include: implementation of action plan, amount and source of funding allocated for the implementation of tobacco control programs, size of the program and organization, and number of staff dedicated to support programmatic activity. Funding-related information will be collected from annual progress reports of state health departments, annual reports, and funding opportunities of funding agencies relevant to tobacco control. Abstraction will include only records that are publically available and only programmatic and organizational information will be recorded. No individual identifying information will be recorded.

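### The plan names rater-subjectivity bias in record abstraction but does not mask the two evaluators to arm, and its agreement checks and standardized tools cannot detect a bias both raters share

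*Combined protocol and SAP*

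**What the plan says.** Section 5.1, Phase 2, describes two sources that pass through evaluators.

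- **Program records.** Under Step 2, "data will be abstracted by two trained evaluators using standardized methods and data collection tools created by the research team". Step 3 states the hazard: "Data collected via record review and abstraction are subject to bias that may result from rater subjectivity". The response in the same step is that "a baseline reliability evaluation will be conducted early in the process to calculate inter-rater reliability", with further checks at two later time points. Step 2 also relies on the form itself: "The development and use of a standardized instrument for the review and abstraction will improve inter-rater reliability". A comparison across sources is planned, with a different purpose: "In order to determine validity of self-reported data from the PSAT, agreement between self-reported and record-based information will be assessed".
- **Key informant interview and survey.** Step 2 uses a standard script with multiple-choice questions answered by the program manager, and says "We will record phone interviews to ensure comprehensive analysis by trained abstracters". Step 3 repeats the hazard: "Data collected via interview/survey and abstraction are subject to bias that may result from rater subjectivity".

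Section 10.0, Data abstraction, restricts abstraction to public records and describes the content: "Examples of variables of interest include: implementation of action plan, amount and source of funding allocated for the implementation of tobacco control programs", followed by program size and staff numbers. The same section counts completion and implementation of the action plan as part of dosage received.

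The only concealment described is in section 3.0 and the comparison state protocol in section 5.1: states learn their group after completing the baseline PSAT. This concerns the states, and it has ended before either follow-up. Nothing is said about what the evaluators, interviewers or coders know, or whether they also run workshops or quarterly technical assistance calls.

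**The concern.** Two raters can agree perfectly and both be wrong in the same direction. Inter-rater reliability measures how far raters differ from each other. It carries no information about an error they have in common. If both evaluators know which states were trained and both resolve doubtful entries in those states' favour, agreement stays high and the arm difference is inflated.

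This matters because Phase 2 names program records as the source for predictors of sustainability and for institutionalization, and describes institutionalization and sustainability as the dependent variable. Step 1 of the abstraction also gives records a second job: supporting the PSAT responses and exposing bias in them. PSAT respondents and program managers will know their arm at follow-up and cannot be masked. Abstraction of records is a step where the assessor could be. If it is done with knowledge of arm, a check meant to expose bias in the self-reports may lean the same way.

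**Working it through.** **1. Set the hazard against each safeguard.** The question for each is whether it would detect or prevent an arm-related shift shared by both raters.

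| Safeguard | Where | Detects or prevents a shared shift? |
|---|---|---|
| Inter-rater reliability at three time points | 5.1, Step 3 (records and interview) | No; it sees only differences between raters |
| Standardized abstraction instrument | 5.1, records, Step 2 | Narrows discretion; its stated gain is better agreement |
| Scripted multiple-choice questions, recorded calls | 5.1, interview, Step 2 | Largely, for interview items, because the manager chooses the answer |
| Agreement of PSAT with records and interview | 5.1, Step 3 | No; aimed at validating the PSAT |
| Public records only | 10.0 | No; limits the source, not the rater |
| Group assignment withheld from states until after the baseline PSAT | 3.0; 5.1 | No; concerns states, and baseline only |

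**2. The plan's own sample size.** Section 9.0 (C.6.d) gives an effect size of 1.25, power 0.8, α = 0.05 and about 9 programs per group, raised by one-third to 12. A two-sample t-test with the noncentral t distribution gives n = 9 one-sided (8.68 before rounding; power 81.4% at 9) and n = 12 two-sided (11.09 before rounding; power 70.2% at 9). The stated 9 is therefore reproduced one-sided, which matches the direction of Hypothesis 1, and 9 × 4/3 = 12. The point does not depend on this figure. It supplies the 12 per group used below.

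**3. Illustration of a shared shift.** Assume no true effect, a two-sample t-test with 12 per group (22 degrees of freedom), and a shift of b standard deviations that both raters give to trained states. The noncentrality is δ = b × √(12/2) = b × 2.449. The one-sided rejection rate is the probability that a noncentral t with 22 degrees of freedom and noncentrality δ exceeds the 95th percentile of the central t.

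For agreement, assume true scores with variance 1 and independent rater error with variance 1/9, so that reliability is 1/(1 + 1/9) = 0.90. With equal arms, the shift adds about b²/4 to the variance between states, so the ICC is approximately (1 + b²/4)/(1 + b²/4 + 1/9). At b = 0.5 this is 1.0625/1.1736 = 0.905. The last column is the mean ICC(2,1) over 4,000 simulated trials of 24 states.

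| b (SD) | δ | Rejection, one-sided 5% | Rejection, two-sided 5% | ICC, formula | ICC, simulated |
|---|---|---|---|---|---|
| 0 | 0 | 5.0% | 5.0% | 0.900 | 0.892 |
| 0.25 | 0.612 | 14.7% | 9.0% | 0.901 | 0.893 |
| 0.5 | 1.225 | 32.4% | 21.6% | 0.905 | 0.898 |
| 1.0 | 2.449 | 76.7% | 64.9% | 0.918 | 0.912 |

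The false-positive rate climbs while agreement stays level or improves slightly, because the shift adds to the spread between states and not to the difference between raters. The values of b and the 0.90 reliability are assumptions. The documents give neither, and the planned analysis is a longitudinal regression, not this t-test. The table shows the mechanism; it does not estimate the bias.

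**4. Which items are exposed.** The examples in section 10.0 are mostly amounts and counts. Action-plan implementation is the one listed that plainly calls for judgement. Step 1 says the link between reporting requirements and outcomes is set out in an appendix that is not in the text available here, so the share of judgement-based items cannot be determined.

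**The case against.** Much of the case against a broad criticism is right.

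- A reader might infer that inter-rater agreement is the only safeguard. It is not, as the first table shows. None of the others masks the raters.
- A reader might infer that the evaluators belong to the team that built and delivers the curriculum. The text says only that the research team created the tools. It does not say who the evaluators are, and silence on masking does not prove that they know the arm.
- A reader might extend the point equally to the interview. There the manager picks from fixed options, so coding adds little. The larger exposure is a respondent who knows the arm, and masking coders leaves that untouched.
- A reader might treat records as independent of the participants. The main record source is the annual progress report that each state program itself submits to CDC. Masking abstracters cannot correct what is written there.
- A reader might suppose that action-plan implementation gives away the arm. Sections 1.0 and 5.1 weaken this: CDC requires a sustainability plan from all funded states, and comparison states may carry one out on their own. It is a possible cue, not a reliable one.

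What remains is narrower. The plan identifies rater subjectivity as a source of bias, its stated response cannot reveal the shared form of it, and no masking or separation of roles is described.

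**Conclusion.** The point holds for record items that need judgement. The plan leaves open whether the two evaluators know group assignment and whether they help deliver the training, and its reliability checks and standardized tools would not show an arm-related bias common to both. A shift favouring trained states is plausible, but neither its presence nor its size can be established from the documents. The 14.7% and 32.4% one-sided error rates rest on assumed shifts of 0.25 and 0.5 SD in the whole analysed outcome. Items that are amounts or counts would dilute any such shift.

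The documents do not support the wider conclusion that every outcome is assessed with knowledge of arm. The baseline PSAT is completed before states learn their group, and the evaluators' knowledge is simply not stated. This is a worthwhile and inexpensive improvement to the design, not a defect that invalidates the outcomes. It has to be in place before follow-up abstraction, because knowledge of arm cannot be undone.

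**What to change.** In section 5.1, Program record abstraction, Step 2, and for any coding of recorded calls under Key Informant Interview and Survey, Step 2, state that:

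1. The two planned evaluators are not told group assignment and take no part in workshops or technical assistance.
2. Outcome items are abstracted and locked first. Action-plan implementation and other dose items are abstracted afterwards, on a separate form.

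It would also help to list the record items that need judgement, so that readers can see where the protection matters. Asking evaluators to record a guess of arm at each follow-up is optional; it would let the success of masking be reported.

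The cost is a divided form and a separation of roles between people already planned for. Those two evaluators could not support technical assistance; the documents give no staffing numbers from which to judge how much that matters. Masking will be incomplete where a record mentions the training, and bias in the programs' own reporting will remain, so the report of results should state both limits.

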5.2 Administration

Not applicable.

5.3 Schema

Plans, Actions, and Capacity to Sustain Tobacco Control

**5.4 Dose Modification**

Not applicable.

5.5 Duration of Therapy

Not applicable

5.6 Supportive Care

Not applicable

6.0 Response Assessment

Not applicable

7.0 Study Parameters

Not applicable

8.0 Drug Formulation and Procurement

Not applicable

9.0 Statistical Considerations

C.6.d Statistical power

To estimate the sample size needed for the study, an a priori power analysis was performed using data from a natural experiment. The data consists of Pre and Post PSAT averages from previous work with five tobacco control programs that received action planning and training, and five programs that did not receive action planning or training for which pre- and post-PSAT scores are available. To determine effect size, t-tests of differences-in-means were conducted for the two groups using the changes in PSAT scores between the Pre and Post PSAT data. The standardized differences and t-statistics yielded an effect size of 1.25, which is a large effect size according to Cohen's criteria.¹⁰⁷ Using R statistical environment with packages from Del Re¹⁰⁸ and Champely,¹⁰⁹ the effect size with power = 0.8 and $\alpha = 0.05$ project the necessary sample size to be approximately 9 (programs) per group. Since these calculations are based on a natural experiment, which we note occurred over a period of time that also saw changes to the recommended action planning,² we are careful not to overstate the anticipated power and therefore conservatively propose a sample size one-third larger than calculated, 12 per group as shown in Figure 4. This sample is also sufficient to measure the main goal of the study, to discern whether the training, and accompanying PSAT tool, significantly increase institutionalization of state TC programs.^{108–110}

C.6.e. Data analyses. Descriptive statistics will be calculated (e.g., frequencies and measures of central tendency and dispersion), for both the intervention and comparison group at each of the three data collection time points to assess baseline averages and changes. Multiple comparisons across groups and times will be drawn for independent and dependent variables. All continuous measures will be examined for non-normality and all relationships will be examined for linearity where applicable. Strategies for addressing issues encountered will be applied as necessary such as different functional forms, category scaling, and robust error calculations. In addition, the dose reception and delivery, and participant measures from Aim 1 (C.5.d.) will be used to calculate rates of adoption and implementation of training recommendations (intervention states) and other potential actions taken (comparison states, C.5.e).

[figure not shown]
To incorporate the influence of idiosyncratic characteristics of the state programs, longitudinal regression analysis will be used to model the outcome for each of the dependent variables. This analysis is modeled in Equation 1.

$$\beta_0 + \beta_1 PSAT_{i,t=0} + \beta_2 G_i + \beta_3 D_{it} + \beta_4 (G_{it} * D_{it}) + B_{5-k} X_{it} = Y_{it}$$

Equation 1

where i = state, t = time 1 or 2, $PSAT_{i,t=0}$ = baseline PSAT score, G_i = group (intervention or comparison), D_{it} = dose variable, $(G_{it} * D_{it})$ = an interaction between the group and dose terms, X_{it} = a vector of programmatic, organizational, community and funder variables, and Y_{it} = the

Figure 4. Sample size and power calculation

outcome variable. This analysis will ultimately be used to test Hypothesis 1, that the impact of the training is nonzero and positive.

$$H_0: \hat{\beta}_{intervention} = 0 \quad H_a: \hat{\beta}_{intervention} > 0$$

Hypothesis 1

The multivariate approach allows us to account for the numerous influences found in programmatic, organizational, community, and funder attributes. Data collection at different time points also allows for measuring changes in these variables, and the influence these changes have on institutionalization outcomes. In addition, the level of adoption and implementation of action plans both from the training (intervention states) and from other initiatives (comparison states) will vary across programs and time. Varying levels of action plan implementation across states must be acknowledged. Multivariate longitudinal analyses also allow us to control for differing degrees of dosage reception and delivery. We have successfully used similar dose variables.^{111,112}

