(Aim 2): Demonstrate change in sustainability outcomes in states who received the Program Sustainability Action Planning training compared to states who did not.

The overall goal for the Program Sustainability Action Planning Training and subsequent dissemination activities is to increase capacity for sustainability of evidence-based state TC programs through the institutionalization of the program. To determine the extent of reaching this goal, we will design a randomized effectiveness trial to document differences in organizational and programmatic measures and Program Sustainability Assessment Tool scores between intervention and comparison states. We will rely on three sources of data for this study: 1) state-level program records for measures of predictors of sustainability and institutionalization,^{9,11} 2) PSAT scores and 3) a key informant interview and survey with state program managers. While we anticipate that our study will impact behavioral risk factors for tobacco-related diseases (e.g., rates of smoking and initiation), the dependent variable for our study involves measures of program institutionalization and sustainability.

C.6.a. Data collection methods

Pre-Introduction to Sustainability Webinar Survey

All participants will receive an optional Qualtrics survey via email, prior to participating in the “Introduction to Sustainability” webinar. Participants will be asked program sustainability perception questions, as well as demographic questions (age, gender, race, per NIH reporting requirements). Personally identifiable information, such as the participant’s name, will not be collected.

Program Sustainability Assessment Tool (PSAT)

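### Must the statement that 12 states per group also suffices for institutionalization be changed, when only PSAT change was powered?

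*Combined protocol and SAP*

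**What the plan says.** In Section 9.0, C.6.d the effect size of 1.25 was obtained "using the changes in PSAT scores between the Pre and Post PSAT data" in two sets of five programs. With power 0.8 and alpha 0.05 this gave about 9 programs per group. Because the source was a natural experiment, the authors "conservatively propose a sample size one-third larger than calculated, 12 per group as shown in Figure 4". The next sentence extends the result to institutionalization: "This sample is also sufficient to measure the main goal of the study". Its references (108 to 110 in Section 11.0) are an effect-size package, a power package and the R software.

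Section 5.1, Phase 2 lists three data sources. PSAT scores are one. Another is "state-level program records for measures of predictors of sustainability and institutionalization". The third is an interview and survey of state program managers, for which "Each question is formatted in multiple choice". The record abstraction text says reporting requirements are linked to "established predictors of sustainability and outcomes in Appendix C".

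Section C.6.e says that "longitudinal regression analysis will be used to model the outcome for each of the dependent variables" (Equation 1), and it states one directional hypothesis, that the training effect is positive.

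**The concern.** A standardized effect belongs to the outcome it was measured on. The 1.25 is a difference in self-rated PSAT change divided by the SD of that change. Records and manager answers have their own spread and may respond differently to training. The plan itself uses the records as a check on possible bias in PSAT answers, which suggests the two are not interchangeable. The word *also* marks institutionalization as a second target, yet nothing but software is cited for it.

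Two misreadings are possible. A null institutionalization result might be taken to come from a test known to be well powered. Or, with several dependent variables and the sentence "Multiple comparisons across groups and times will be drawn for independent and dependent variables", one isolated positive result might be taken to confirm the main goal.

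**Working it through.** **Inputs from C.6.d:** d = 1.25, power 0.80, alpha 0.05 (sidedness not stated there; Hypothesis 1 in C.6.e is directional), equal groups, 12 planned per group.

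**Method.** Two-sample t-test with n per group: df = 2n − 2, noncentrality = d·√(n/2), power from the noncentral t distribution.

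**1. The plan's own figure.**
- One-sided: n = 8 gives 76.8% and n = 9 gives 81.4%. The exact solution is 8.68, so 9 per group. The stated figure reproduces.
- Increase by one third: 9 × 4/3 = 12, as stated.
- At n = 12: noncentrality = 1.25 × √6 = 3.06, df = 22, power 90.7%.
- If alpha were two-sided, the solution is 11.09, so 12 per group, with power 83.3%. The final 12 meets 80% power for PSAT change on either reading.

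**2. What 12 per group delivers for another continuous outcome.** Setting power to 0.80 at n = 12 and solving for d gives 1.048 one-sided and 1.197 two-sided, in SDs of that outcome across states within a group. As fractions of the PSAT effect: 1.048/1.25 = 0.84 and 1.197/1.25 = 0.96. The sufficiency sentence is therefore true for this test if the standardized effect on institutionalization is at least 84% (one-sided) or 96% (two-sided) of the PSAT effect.

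**3. Range of assumed institutionalization effects at 12 per group** (the documents give none):

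| Assumed effect (SD) | Power, one-sided | Power, two-sided |
|---|---|---|
| 0.5 | 32% | 22% |
| 0.8 | 60% | 47% |
| 1.0 | 77% | 65% |
| 1.25 | 91% | 83% |

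For 0.8 SD, 80% power would need 21 (one-sided) or 26 (two-sided) per group.

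**4. Limits of these figures.** They describe an unadjusted comparison with all 24 states retained. Equation 1 adds baseline PSAT, dose, a group-by-dose term and covariates, over two follow-up times. Repeated measures can improve precision, and regressors correlated with group can worsen it. With the interaction present, the group coefficient is the effect at zero dose unless dose is centred. The 1.05 and 1.20 SD are therefore not the power of the planned model.

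**5. How far apart the two targets are.** The Background and Objectives sections give the overall goal as greater capacity for sustainability, and Sections 5.1 and 10.0 describe the PSAT as the measure of that capacity. Appendix A includes an item, under Organizational Capacity, on how well the program is integrated into its parent organization. The calculation thus bears directly on the overall goal and partly on institutionalization.

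**The case for a change.** The strongest case for acting is that the authors say they take care not to overstate power, and the next sentence then does so for what it calls the main goal. The wording could be corrected cheaply, with the sample size untouched. Figure 4 is cited only for the PSAT sizing, and Appendix C is described as a map of reporting requirements, so neither is an obvious home for a missing institutionalization calculation.

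It stands that the sentence has no numerical support in the text. It does not follow that the sample is too small, since no document figure for institutionalization contradicts 12 per group. A replacement sentence quoting 1.05 SD would gain little, because it would describe a t-test that the plan does not use for Hypothesis 1.

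The worry about several outcomes is a separate matter and less secure. Figure 4, Appendix C and sections C.6.b and C.6.c are not in the text available here, so the absence of a named primary outcome cannot be asserted. The sentence on multiple comparisons follows directly on descriptive statistics and covers independent variables too, so it can be read as descriptive. The missing sidedness label is a clarification, because 9 per group is the correct one-sided answer and agrees with Hypothesis 1.

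**Conclusion.** No change to the plan follows. The power statement is supported for PSAT change and unsupported, though not contradicted, for institutionalization. No stated power or sample size fails to be delivered: 9 per group reproduces, and 12 per group gives 90.7% (one-sided) or 83.3% (two-sided) for the assumed 1.25. The sufficiency sentence sets no sample size, test or decision rule, so narrowing it would alter nothing that is done in the trial. Analysts can fill the gap by reporting institutionalization estimates with confidence intervals and by not treating a null result as evidence of no effect. For scale, the smallest difference with 80% power is about 1.05 SD one-sided or 1.20 SD two-sided, assuming an unadjusted two-group t-test on a continuous outcome with all 24 states retained.

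### Hypothesis 1 is tested on several dependent variables with no primary test, no identified coefficient and no error control, although the trial was sized for one test of PSAT change

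*Combined protocol and SAP*

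**What the plan says.** All references are to the Combined protocol and SAP.

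- **Outcomes (5.1 Treatment Plan, Phase 2).** The plan states that "the dependent variable for our study involves measures of program institutionalization and sustainability". The data come from three sources: program records, PSAT scores, and a manager interview and survey.
- **Model (9.0, C.6.e).** The plan says that "longitudinal regression analysis will be used to model the outcome for each of the dependent variables". Equation 1 covers follow-up times 1 and 2. It contains baseline PSAT, a group term (beta 2), a dose term (beta 3), a group-by-dose term (beta 4) and covariates. It is used to test Hypothesis 1, whose alternative is that the intervention coefficient is greater than zero.
- **Other comparisons (9.0, C.6.e).** After the sentence on descriptive statistics, the plan adds: "Multiple comparisons across groups and times will be drawn for independent and dependent variables".
- **Sample size (9.0, C.6.d).** The effect size was obtained "using the changes in PSAT scores between the Pre and Post PSAT data" in five trained and five untrained programs: "The standardized differences and t-statistics yielded an effect size of 1.25". This gave about 9 programs per group, raised to 12. The section continues: "This sample is also sufficient to measure the main goal of the study", and identifies that goal as increased institutionalization.

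The available text names no primary outcome, primary time point, order of testing or multiplicity adjustment. It does not say which term of Equation 1 is the intervention coefficient in Hypothesis 1.

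**The concern.** One conclusion, that the training works, is attached to a model fitted to several outcomes. Alpha is mentioned once, in the power section, and applies there to a single test. Without a rule saying which result decides the question, the outcome carrying the conclusion can be chosen after the data are seen. The choice of coefficient is open in the same way.

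The plan also points two ways on which outcome matters most. PSAT change is the outcome with a sample-size calculation, while institutionalization is the stated main goal. A reader therefore cannot work out the primary test by inference.

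Two things are at stake: the error rate behind a positive claim that the team intends to disseminate widely, and a statement of adequate sample size that its own calculation does not cover.

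**Working it through.** **Inputs.** From C.6.d: standardized effect d = 1.25 on PSAT change, power 0.80, alpha 0.05 (sidedness not stated), 9 per group calculated, 12 per group planned. From C.6.e: a one-sided alternative in Hypothesis 1. The number of dependent variables, k, is not given and is assumed below. So is the correlation between their test statistics.

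**Step 1: reproduce the stated 9 per group.** For a two-sample t-test, power comes from the noncentral t distribution with 2n - 2 degrees of freedom and noncentrality d × sqrt(n/2).

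- One-sided 0.05, power 0.80: n = 8.68, which rounds up to 9. This matches.
- Two-sided 0.05, power 0.80: n = 11.09, which rounds up to 12. This does not match.

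The stated figure is therefore that of one one-sided test on one outcome. Raising it by one-third gives 9 × 4/3 = 12.

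**Step 2: power of one test at 12 per group.** The noncentrality is 1.25 × sqrt(12/2) = 3.06 with 22 degrees of freedom. Power is 90.7% one-sided and 83.3% two-sided.

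**Step 3: chance of at least one false positive across k outcomes, each tested one-sided at 0.05.** For independent tests it is 1 - 0.95^k:

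- k = 2: 1 - 0.9025 = 9.8%
- k = 3: 1 - 0.8574 = 14.3%
- k = 4: 1 - 0.8145 = 18.6%

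For correlated tests, equicorrelated normal statistics were simulated as sqrt(rho) × U + sqrt(1 - rho) × E_j, with 200,000 draws. The chance is the share of draws in which any statistic exceeds the one-sided 5% limit.

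| Outcomes (k) | rho = 0.8 | rho = 0.5 | rho = 0 |
|---|---|---|---|
| 2 | 7.6% | 8.8% | 9.8% |
| 3 | 9.3% | 11.8% | 14.3% |
| 4 | 10.5% | 14.4% | 18.6% |

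The rate is above 5% for any k of 2 or more unless the tests are perfectly correlated.

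**Step 4: cost of splitting alpha instead of naming one test.** With a Bonferroni split, 12 per group and d = 1.25 on every outcome, one-sided power per outcome is 83.3% for k = 2, 78.1% for k = 3 and 74.0% for k = 4. From three outcomes on it falls below the plan's 80%.

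**Step 5: institutionalization.** C.6.d gives no effect size, variance or sample-size result for any institutionalization measure. Its only described calculation uses PSAT change, so the adequacy statement for the main goal cannot be reproduced.

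**The case against.** A sponsor could fairly make five points.

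1. **Hypothesis 1 is not tested separately at each follow-up.** This is correct. Equation 1 pools times 1 and 2 and has no time term and no group-by-time term. The sentence on multiple comparisons follows the one on descriptive statistics, also covers independent variables, and is not tied to Hypothesis 1.
2. **The number of outcomes is unknown, so the inflation may be modest.** This is also correct. With two outcomes correlated at 0.9, the one-sided rate is 6.7%.
3. **No rule says that one significant outcome is enough.** True; the plan leaves the decision rule open. The rates above are therefore conditional on that use.
4. **An outcome list may exist elsewhere.** The program record abstraction text in 5.1 cites an appendix linking reporting requirements to predictors and outcomes. It is not in the text available, and Figure 4 is not shown. A list there could fix k. Nothing in the description of that appendix suggests that it names a primary test.
5. **Making PSAT primary demotes the stated main goal.** It does, and that is a real cost.

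A reader might go further and count the overall PSAT score plus its eight domains as nine tests, or eighteen over two follow-ups. Independent tests at 5% would then give 1 - 0.95^9 = 37% or 1 - 0.95^18 = 60%. The documents do not support this reading. They describe aggregation to one overall score per state, nowhere say that domain scores will be compared between groups, and pool the follow-ups for Hypothesis 1.

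None of these points supplies a primary test, identifies the coefficient or adds error control.

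**Conclusion.** The point holds in limited form. Hypothesis 1 is applied to more than one dependent variable, while the available text has no primary outcome, no identified coefficient and no error control. If any significant outcome is taken to support the claim, the false-positive chance is above 5%: about 8-10% for two outcomes, 9-14% for three and 11-19% for four. These ranges assume one-sided 5% tests and correlation from 0.8 down to 0. The true figure cannot be fixed from the documents, and a reader who infers that it must be many times 5% goes beyond them.

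Separately, the statement that 12 per group is enough for institutionalization is unsupported, because the calculation described covers PSAT change only. This does not show that the sample is too small for institutionalization, only that adequacy has not been demonstrated.

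**What to change.** Before analysis, amend section 9.0 as follows.

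1. **Primary test.** Name the group coefficient for overall state PSAT, adjusted for baseline PSAT. State whether it is taken at one named time point or as the pooled follow-up contrast, and whether the test is one- or two-sided. Map it explicitly to a term of Equation 1 and say whether the dose terms stay in that model. With the group-by-dose term included, beta 2 is the group difference at zero dose. Under the sponsor's d = 1.25 with 12 per group, a simple two-group test of change has 91% power one-sided or 83% two-sided.
2. **Secondary tests.** List a few named institutionalization measures and test them with Holm adjustment.
3. **Other comparisons.** Report the comparisons across groups and times as estimates with intervals.
4. **Sample-size text.** Limit the adequacy statement to PSAT change.

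The change is to analysis-plan wording only. Some secondary results can no longer be declared at an unadjusted 5%. Institutionalization, the stated main goal, becomes a secondary test because it has no power calculation.
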